Chronic disease: In the case of disease (excluding disease under study) that is progressing by episodes (chronic disease), if the disease is known when the participant enters the trial, only worsening (increased frequency or intensity of the episodes or attacks) will be documented as an AE. If the disease is detected during the trial, and if repeated episodes enable diagnosis of a chronic disease, the episodes will be entered with the diagnosis and start/stop dates grouped together, and clearly described in the source documents.

Disease under study (Pemphigus): Unexpected progression, signs, or symptoms of the disease under study are not AEs and are not to be recorded on the AE page of the CRFs unless the event meets the definition of an SAE or is not consistent with the typical clinical course of the patient's disease as established by the patient's medical history. Worsening of the disease under study or other disease-related symptoms should be recorded as an AE only if the event meets the definition of an SAE or is not consistent with the typical clinical course of the disease.

Laboratory Out of Range Values: An isolated, out-of-range laboratory result in the absence of any associated, clinical finding may or may not be considered an AE; the Investigator's evaluation should be based on a consideration of the overall clinical context. An out-of-range laboratory result will be considered clinically significant and recorded as an AE when it is part of a clinical abnormality requiring specific medical intervention or follow-up. The test will be repeated and the patient will be followed-up until the test value has returned to the normal range or baseline, or the Investigator has determined that the abnormality is chronic or stable. The Investigator will exercise medical judgment in deciding whether out-of-range values are clinically significant and document the assessment in the source records.

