3.4.3 Pre-treatment vs. treatment emergent vs. post last dose adverse events

Pre-treatment events are the events that started prior to the first study drug dosing.

Treatment emergent adverse events (TEAEs) are the events started on or after the first study drug.

Post last dose adverse events are the events that started after the last date of study drug dosing.

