4 STATISTICAL METHODS

4.1 Safety Endpoints

The incidence of treatment-emergent AEs (TEAEs), including clinically significant changes in physical examination, laboratory tests, and vital signs.

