5.5.1 Adverse Events

TEAEs will be attributed to the dose level where the adverse event start date is on or after the start date of that dose level and before the next dose level if applicable.

Adverse events with preferred term (PT) = “Pemphigus” will be excluded from the TEAE tables. All pemphigus PT are Disease Under Study and will be documented in a separate summary table and a separate patient data listing labeled as Disease Under Study Events.

A summary of adverse events by dose level and overall will include:

- The number of pre-treatment AEs and the number/percentage of patients reporting at least one pre-treatment AE
- The number of pre-treatment SAEs and the number/percentage of patients reporting at least one pre-treatment SAE
- The number of TEAEs and the number/percentage of patients reporting at least one TEAE
- The number of post last dose adverse events and the number/percentage of patients reporting at least one post last dose adverse event
- The number of related TEAEs and the number/percentage of patients reporting at least one related TEAE
- The number of serious TEAEs and the number/percentage of patients reporting at least one serious TEAE
- The number of related serious TEAEs and the number/percentage of patients reporting at least one related serious TEAE

- The number of TEAEs leading to study discontinuation and the number/percentage of patients reporting at least one TEAE leading to study discontinuation
- The number of deaths and the number/percentage of patients reporting at least one TEAE death
- The number/percentage of patients reporting TEAEs by Action Taken with Study Drug
- The number/percentage of patients reporting TEAEs by the maximum grade

TEAEs will be summarized by SOC and PT by dose level and overall. Patients with multiple events within a particular SOC or PT within each dose level will be counted once within that dose level. The number of episodes of events for each SOC and PT will also be displayed. The same tabulation will be performed for related TEAEs, SAEs and AE leading to study drug discontinuation.

TEAEs will also be summarized by the maximum intensity grade (Grade 1 to 5), SOC and PT. Patients with multiple events within a particular SOC or PT will be counted once under the maximum intensity grade. The same tabulation will be performed for related TEAEs.

Patient data listings will be generated for:

- Prior adverse events
- Prior SAE
- TEAEs
- Related TEAEs
- SAEs

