Table B.14.2.2.51.2 Anti-DSG 3 – Actual Values, Change and Percent Change from Baseline – Overall and by Baseline Value (Completer Population)

Table B.14.2.2.51.3 Anti-DSG 3 – Actual Values, Change and Percent Change from Baseline – Overall and by Baseline Value (PP Population)

Table B.14.3.1.1 Summary of Adverse Events (Safety Population)

	400 mg QD (N = n)	400 mg BID (N = n)	600 mg BID (N = n)	Post Last Dose (N = n)	Overall (N = n)
Number of Pre-treatment AEs					x
Number (%) of patients with at least one Pre-treatment AE					x (x.x)
Number of Pre-treatment SAEs					x
Number (%) of patients with at least one Pre-treatment SAE					x (x.x)
Number of Treatment Emergent Adverse Events (TEAE)	x	x	x	x	x
Number (%) of patients with at least one TEAE	x (x.x)	x (x.x)	x (x.x)	x (x.x)	x (x.x)
Number of Related TEAEs	x	x	x	x	x
Number (%) of patients with at least one Related TEAE	x (x.x)	x (x.x)	x (x.x)	x (x.x)	x (x.x)
Number of Treatment Emergent SAEs	x	x	x	x	x
Number (%) of patients with at least one Treatment Emergent SAE	x (x.x)	x (x.x)	x (x.x)	x (x.x)	x (x.x)
Number of Related Treatment Emergent SAEs	x	x	x	x	x
Number (%) of patients with at least one Related Treatment Emergent SAE	x (x.x)	x (x.x)	x (x.x)	x (x.x)	x (x.x)
TEAE - Action taken with study drug – Number (%) of patients*					
Dose not changed	x (x.x)	x (x.x)	x (x.x)	x (x.x)	x (x.x)
Dose reduced	x (x.x)	x (x.x)	x (x.x)	x (x.x)	x (x.x)
Study drug interrupted	x (x.x)	x (x.x)	x (x.x)	x (x.x)	x (x.x)
Study drug discontinued	x (x.x)	x (x.x)	x (x.x)	x (x.x)	x (x.x)

Table B.14.3.1.1 Summary of Adverse Events (Safety Population)

	400 mg QD (N = n)	400 mg BID (N = n)	600 mg BID (N = n)	Post Last Dose (N =n)	Overall (N = n)
Not applicable	x (x.x)	x (x.x)	x (x.x)	x (x.x)	x (x.x)
Unknown	x (x.x)	x (x.x)	x (x.x)	x (x.x)	x (x.x)
TEAE - Maximum Intensity of TEAE – Number (%) of patients					
Grade 1	x (x.x)	x (x.x)	x (x.x)	x (x.x)	x (x.x)
Grade 2	x (x.x)	x (x.x)	x (x.x)	x (x.x)	x (x.x)
Grade 3	x (x.x)	x (x.x)	x (x.x)	x (x.x)	x (x.x)
Grade 4	x (x.x)	x (x.x)	x (x.x)	x (x.x)	x (x.x)
Grade 5	x (x.x)	x (x.x)	x (x.x)	x (x.x)	x (x.x)

Patients are classified into different dose levels according to the dose they received at the start of AE.

Percentages are based on the number of patients in each dose group and overall.

Adverse events where PT='Pemphigus' are excluded from this table.

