Adverse events are sorted by overall descending frequency of SOC and within each SOC, by overall descending frequency of PT.

Patients with multiple events within a particular SOC or PT will be counted once under the maximum intensity grade.

Program: <program name (date, time)>, Path: <path>

Programming note: Repeat table for the 400 mg QD, 400 mg BID and 600 mg BID, Post Last Dose groups.

Table B.14.3.1.6 Serious Treatment Emergent Adverse Events by SOC and PT (Safety Population)

System Organ Class (SOC) Preferred Term (PT)	400 mg QD (N = n)		400 mg BID (N = n)		400 mg BID (N = n)		Post Last Dose (N = n)		Overall (N = n)	
	n (%)	[E]	n (%)	[E]	n (%)	[E]	n (%)	[E]	n (%)	[E]
Patients with at least one SAE	x (x.x)	x	x (x.x)	x	x (x.x)	x	x (x.x)	x	x (x.x)	x
SOC1	x (x.x)	x	x (x.x)	x	x (x.x)	x	x (x.x)	x	x (x.x)	x
PT1.1	x (x.x)	x	x (x.x)	x	x (x.x)	x	x (x.x)	x	x (x.x)	x
PT1.2	x (x.x)	x	x (x.x)	x	x (x.x)	x	x (x.x)	x	x (x.x)	x
PT1.3	x (x.x)	x	x (x.x)	x	x (x.x)	x	x (x.x)	x	x (x.x)	x
SOC2	x (x.x)	x	x (x.x)	x	x (x.x)	x	x (x.x)	x	x (x.x)	x
PT2.1	x (x.x)	x	x (x.x)	x	x (x.x)	x	x (x.x)	x	x (x.x)	x
PT2.2	x (x.x)	x	x (x.x)	x	x (x.x)	x	x (x.x)	x	x (x.x)	x
PT2.3	x (x.x)	x	x (x.x)	x	x (x.x)	x	x (x.x)	x	x (x.x)	x
...etc...										

Patients are classified into different dose levels according to the dose they received at the start of AE.

Percentages are based on the number of patients in each dose group and overall.

Adverse Events were coded using MedDRA, Version 18.0.

Serious adverse events where PT='Pemphigus' are included in this table.

Adverse events are attributed to the dose level where the AE start date is on or after the start date of the dose level, but before the next dose level, if applicable.

Treatment emergent adverse events are the events started on or after the first dose of study drug and prior to the date of last dose of study drug.

Adverse events are sorted by overall descending frequency of SOC and within each SOC, by overall descending frequency of PT.

Program: <program name (date, time)>, Path: <path>

Table B.14.3.1.7 Treatment Emergent Adverse Events Leading to Study Drug Discontinuation by SOC and PT (Safety Population)

System Organ Class (SOC) Preferred Term (PT)	400 mg QD (N = n)		400 mg BID (N = n)		600 mg BID (N = n)		Post Last Dose (N = n)		Overall (N = n)	
	n (%)	[E]	n (%)	[E]	n (%)	[E]	n (%)	[E]	n (%)	[E]
Patients with at least one TEAE leading to study drug discontinuation	x (x.x)	x	x (x.x)	x	x (x.x)	x	x (x.x)	x	x (x.x)	x

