Treatment emergent adverse events are the events started on or after the first dose and prior to the date of last dose of study drug.

If Date >= first dose date, then Study Day = (Date - Date of first dose +1). If Date < first dose date, then Study Day = (Date - Date of first dose).

Program: <program name (date, time)>, Path: <path>

Programming note for all TEAE listings: Display "Post last dose" if AE started after date of last study drug dosing

Same listing shell will be used for the following listing:

Listing B.16.2.7.4 Related Treatment Emergent Adverse Events (Safety Population)

Listing B.16.2.7.5 Serious Adverse Events (Safety Population)

Programming note: The following variables will be added to the “SAE” column for the SAE listing: Start Date (ddMMMyyyy) (Study Day), Stop Date (ddMMMyyyy) (Study Day) or Ongoing, Duration (if not ongoing), SAE Criteria

Listing B.16.2.7.6 Treatment Emergent Adverse Events Leading to Study Drug Discontinuation (Safety Population)

Listing B.16.2.7.7 Serious Treatment Emergent Adverse Events Leading to Study Drug Discontinuation (Safety Population)

Starting Dose	Patient ID	Age/ Gender	PRN Dose Level at AE start	SOC: System Organ Class PT: Preferred Term V: Verbatim	Start Date (ddMMMyyyy) (Study Day) Stop Date (ddMMMyyyy) (Study Day) or Ongoing Duration (if not ongoing)	SAE? (Y/N) If yes: Start Date (ddMMMyyyy) (Study Day) Stop Date (ddMMMyyyy) (Study Day) or Ongoing Duration (if not ongoing)	CTCAE Grade	Relationship to Study Drug	Details
400 mg QD	xxxxxxx	xx/F	400 mg QD	SOC: xxx PT: xxx V: xxx	Start: ddMMMyyyy (Day X) Stop: ddMMMyyyy (Day X) Duration: x days Pattern: xxx	Y Start: ddMMMyyyy (Day X) Stop: ddMMMyyyy (Day X) Duration: x days SAE Criteria: xxx Hospitalization: Initial or Prolongation Admission Date: Discharge Date: Date of Death: Cause of Death: Autopsy performed?: Death certificate completed?:	Grade x	xxxx	Action Taken to study drug: xxx Outcome: xxx Has the Cause of the AE been established: Y - xxx Caused study discontinuation?: N or Y Treated for this AE?: Y or N (AE description)

	
Description of SAE: Did the SAE abate after use of study treatment stopped? Did the SAE reoccur after reintroduction of study treatment? Interruption of study treatment: Date stopped: Date restarted: Type of Sequelae: PI rationale for "Not Related":

--	--

F=Female; M=Male

Adverse Events were coded using MedDRA, Version 18.0.

Serious Adverse events where PT='Pemphigus' are included in this listing.

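### Part B removes pemphigus-coded events from its TEAE tables although the protocol records only serious or atypical ones as AEs, and its SAE outputs conflict if a serious one occurs

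*SAP*

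**What the plan says.** Protocol 12.3 treats variation in pemphigus activity as expected and as measured elsewhere. Worsening of the disease under study "should be recorded as an AE only if the event meets the definition of an SAE or is not consistent with the typical clinical course".

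The safety endpoint in Part B SAP 4.1, worded as in protocol 11.1.1, is "The incidence of treatment-emergent AEs (TEAEs), including clinically significant changes in physical examination, laboratory tests, and vital signs". SAP 3.4.3 defines the term by timing alone: "Treatment emergent adverse events (TEAEs) are the events started on or after the first study drug". Neither makes an exception for a preferred term.

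SAP 5.5.1 then sets a further rule for events coded to Pemphigus: they "will be excluded from the TEAE tables. All pemphigus PT are Disease Under Study and will be documented in a separate summary table". It also calls for their own listing.

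The shells in SAP section 6 carry this out unevenly. The footnote "Adverse events where PT='Pemphigus' are excluded from this table" stands under Tables B.14.3.1.1 to B.14.3.1.5 and B.14.3.1.7. Table B.14.3.1.6, serious TEAEs by SOC and PT, has the opposite footnote: "Serious adverse events where PT='Pemphigus' are included in this table". Table B.14.3.1.1, which excludes pemphigus, also has a row headed "Number of Treatment Emergent SAEs". Listing B.16.2.7.7, serious TEAEs leading to discontinuation, states: "Serious Adverse events where PT='Pemphigus' are included in this listing".

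**The concern.** The protocol and the SAP filter the same events in sequence. The protocol's filter is selective: routine flares stay off the AE page, and serious or atypical ones go on it. The SAP's filter works on the preferred term alone, so it removes from the headline safety tables the events that the protocol chose to keep.

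The stakes are the primary safety outcome and the consistency of the SAE count. Part B tests a lower starting dose and admits more severe disease (PDAI up to 60, against 45 in Part A). A serious or atypical flare is therefore an event that a reader of the safety tables would want to find. As the shells stand, a patient whose only TEAE is a serious pemphigus flare would count as having no TEAE and no SAE in the summary table, yet would count in the SAE table.

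**Working it through.** The plan gives no figure to reproduce on this point. The check is mainly a comparison of texts, with short arithmetic for scale.

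**1. How each Part B output treats PT Pemphigus (SAP 5.5.1 and section 6 shells)**

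| Output | Pemphigus events |
|---|---|
| Table B.14.3.1.1, summary (TEAE, SAE, related SAE, action-taken and grade rows) | excluded |
| Tables B.14.3.1.2 to B.14.3.1.5, TEAEs and related TEAEs by PT and grade | excluded |
| Table B.14.3.1.6, serious TEAEs | serious ones included |
| Table B.14.3.1.7, discontinuations | excluded |
| Listing B.16.2.7.5, SAEs (reuses the B.16.2.7.3 shell) | excluded |
| Listing B.16.2.7.6, discontinuations (same shell) | excluded |
| Listing B.16.2.7.7, serious discontinuations | serious ones included |
| Listing B.16.2.7.8, deaths (same shell as B.16.2.7.3) | excluded |
| Listing B.16.2.7.10, Disease Under Study | all included |
| Disease Under Study summary table | promised in 5.5.1, absent from the table list |

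The exclusion footnote of the shared listing shell is replaced only for B.16.2.7.10, so it carries over to the SAE and death listings. The table list runs from B.14.3.1.7 directly to B.14.3.2.1.

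**2. Contradictions that follow**

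- Tables B.14.3.1.1 and B.14.3.1.6 both count treatment-emergent SAEs, under opposite rules.
- SAE Table B.14.3.1.6 and SAE Listing B.16.2.7.5 also follow opposite rules.
- Serious discontinuations are a subset of all discontinuations. Listing B.16.2.7.7 can nevertheless contain an event that is missing from both Table B.14.3.1.7 and Listing B.16.2.7.6.
- A fatal event coded to Pemphigus would be missing from the death listing and from the Grade 5 row of B.14.3.1.1.

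**3. Declaration.** SAP 4.7 lists added populations and changes to secondary endpoints. It does not mention this exclusion. Part A SAP 9.1 has no such exclusion.

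**4. Size**

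Input: 25 patients planned in Part B (SAP 2.3).

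- SAE events: count in B.14.3.1.6 minus count in B.14.3.1.1 equals the number of serious pemphigus TEAEs. It is zero only if none occurs.
- Incidence counts patients with at least one event. Each patient whose only TEAE is a pemphigus event lowers TEAE incidence by 1/25 = 4 percentage points. Each patient whose only SAE is one lowers the SAE incidence in B.14.3.1.1 by the same amount. A patient with another TEAE (or another SAE) changes it by 0.
- The documents give no rate of serious pemphigus TEAEs. For assumed per-patient rates p, the chance that at least one of 25 patients has one, so that the two SAE event counts differ, is 1 − (1 − p)^25: 22% at p = 1%, 40% at 2%, 72% at 5% and 93% at 10%. These rates are assumptions and only show the range.

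**The case against.** The strongest defence is that the events are moved, not lost. SAP 5.5.1 requires a separate table and listing, Listing B.16.2.7.10 covers all of them, and B.14.3.1.6 keeps the serious ones. That stands. A reader might infer that every pemphigus event disappears from reporting, and the documents do not support it. The events missing from all the by-PT TEAE tables are the non-serious, atypical ones.

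It can also be said that worsening is measured as efficacy: time to relapse, time to first PDAI increase, PDAI change and steroid use. Protocol 12.3 uses that reasoning for ordinary variation, yet still keeps serious or atypical events as AEs. The efficacy tables are also an incomplete substitute. SAP 5.4 bases them on the mITT population, which requires treatment to Week 5 and a Week 5 assessment; the supporting Completer and per-protocol sets require later visits. Under protocol Appendix 1B a potentially life-threatening flare leads to stopping PRN1008. If that happens before Week 5, the patient is outside the mITT efficacy tables.

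Three further points are fair. The footnotes state their rules, so a discrepancy could be traced. Section 6 allows the shells to be adjusted, so the missing table may be an oversight. Sites may also record some ordinary flares as AEs, in which case the exclusion would remove more than the serious or atypical ones. None of these explains why two counts with the same label should follow opposite rules.

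A reader might also infer that the exclusion spoils a planned pooling of safety across Parts A and B. The protocol's statements on combining the Parts fall under clinical activity in the synopsis and under efficacy in 11.5.3 and 11.9.1, and no safety pooling is planned. What remains is that the Part A and Part B TEAE rates would not be like for like on this point.

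**Conclusion.** The point holds and should be fixed. The Part B SAP applies to the primary safety outcome an exclusion that neither the protocol's outcome nor the SAP's own TEAE definition contains, and does not declare it. Its SAE, discontinuation and death outputs follow inconsistent rules.

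The effect is conditional. With no pemphigus-coded AE, nothing changes. One serious pemphigus TEAE is enough to make the SAE event counts of B.14.3.1.1 and B.14.3.1.6 differ. The incidence shift is 4 points per patient at 25 patients, and only for a patient with no other TEAE (or no other SAE).

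A reader might be tempted to put a total on the understatement, for instance from the two patients in protocol 1.4.2.1 who temporarily needed high-dose corticosteroid for worsening. The documents do not support that. The sentence does not state its denominator (18 with efficacy data or 21 treated), and worsening that needs steroid is not an AE under 12.3 unless it is serious or atypical.

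This is an open-label pilot with no hypothesis testing and full listings. The defect therefore affects how the safety results read and whether they reconcile; no formal inference depends on it.

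**What to change.** In SAP 5.5.1 and the footnotes of Tables B.14.3.1.1 to B.14.3.1.5 and B.14.3.1.7, and in the matching listing shells, count every pemphigus event that qualifies as an AE under protocol 12.3 in the TEAE, SAE, discontinuation and death outputs. If the sponsor wants a view without the disease under study, add a supplementary row excluding PT Pemphigus.

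At a minimum, apply one inclusion rule to all SAE, discontinuation and death tables and listings, and report TEAE incidence both with and without PT Pemphigus.

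In either case, add the Disease Under Study summary table that 5.5.1 promises, and declare any remaining exclusion in SAP 4.7 as a departure from the protocol's TEAE outcome.

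The cost is SAP and shell wording plus one table already promised. Reported TEAE and SAE rates may be slightly higher.

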5.5.2 Laboratory Data

The following laboratory parameters are measured at visits specified in the Schedule of Assessments (Table 1).

Laboratory Panel	Test Parameters
Hematology	hemoglobin, hematocrit, erythrocyte count (RBCs), thrombocyte count (platelets), leukocyte count (WBCs) with differential in absolute counts (including neutrophils, eosinophils, basophils, lymphocytes, and monocytes)
Coagulation	PT/INR, thrombin time, aPTT, fibrinogen level.
Serum Chemistry	aspartate aminotransferase (AST), alanine aminotransferase (ALT), total, direct, and indirect bilirubin levels, alkaline phosphatase (ALP), albumin, creatinine, urea, total protein, sodium, chloride, calcium, phosphate, potassium, glucose (random), creatine phosphokinase (CPK) and thyroid stimulating hormone (TSH), chloride, calcium, phosphate, potassium, glucose (random), creatinine phosphokinase (CPK) and serum pregnancy
Urinalysis	pH, specific gravity, protein, glucose, ketones, bilirubin, blood, nitrites, urobilinogen and leukocytes measured by dipstick

Laboratory Panel	Test Parameters
Serology	HIV, hepatitis B and hepatitis C and QuantiFERON® TB testing at screening only

Serology tests are only measured at screening. These results will be presented in a patient data listing.

For other laboratory panels, the actual values and change from baseline values in numerical results will be summarized by dose level and overall. For categorical results, the frequency counts and percentages will be tabulated by each dose level and overall.

Shifts from baseline tables will be provided for all laboratory parameters where low/normal/high can be determined by the normal ranges or can be classified as normal/abnormal.

A special group of clinical laboratory tests, including ALT, AST, TBL and ALP, which are believed to be the indicators for drug induced liver injury (DILI) will be assessed separately. Frequency tables will be used to summarize elevations in these parameters. The following criteria will be documented:

- AST > 3x, 5x, 10x and 20x Upper Limit of Normal (ULN)
- ALT > 3x, 5x, 10x, and 20x ULN
- TBL > 1.5x and 2x ULN
- ALP > 1.5x ULN
- ALT or AST > 3x ULN and Total Bilirubin > 1.5x ULN
- ALT or AST > 3x ULN and Total Bilirubin > 2x ULN

Scatter plots of the peak TBL divided by the ULN will be plotted on a log scale against the peak ALT divided by the ULN. Reference lines will be plotted for the ULN for TBL and ALT, 2x ULN for TBL and 3x ULN for ALT. Any patients in the upper right quadrant, which is defined by 2x ULN for TBL and 3x ULN for ALT, would represent cases to be investigate for potential DILI.

Patient data listings will be provided for each laboratory panel and the DILI parameters. Separate listings will be provided for patients with out of range results or abnormal results at any visits.

